- Video 3 (3:06) "Pas soterrani cap a la platja". In motion walking slowly from the end of Calle de Mar to the beach.
 - Video 4 (2:00) "Walking along the Passeig Maritim Badalona Part 1". In motion walking at the beginning of the Passeig Marítim de Badalona.
- Video 5 (2:00) "Walking along the Passeig Maritim Badalona Part 2". In motion walking along the Passeig Marítim.
- Video 6 (3:30) "Walking along the Passeig Maritim Badalona Part 3". In motion walking along the Passeig Marítim from Anis del Mono to Pont del Petroli.
- Video 7 (5:00) "You saw the Pont del Petroli Badalona". Static on a balcony with views of the sea and the Pont del Petroli.
 - Video 8 (5:00) "Badalona Coconut Beach". Static on the Passeig Marítim.
- Cognitive Stimulation Procedure with the videos:
- Method: Visual-verbal stimulation in real time carried out by a researcher who accompanies the session.
- Activity: While watching the videos, the researcher accompanying the session asks the participants to pay attention to specific elements, such as if they recognize the place, how many bicycles they have passed, if they have seen a dog, etc.
- Interrogation:

At the beginning of the session, the type of visualization to be carried out will be entered (*"Next you will watch a video of a square in which you will see different scenes. Stay tuned."*).

While viewing the scenes, you will be asked questions regarding the environment and the elements that appear to encourage attention. ("Do you recognize the square? Have you ever been? What is it called? What are you seeing? Pay close attention to all the details.").

At the end of each video, open and multiple choice questions will be asked. ("Have you seen any animals? How many dogs have you seen passing by, 2 or 5?...") to evaluate attention and memory regarding the elements shown.

- Objectives: The objective of this intervention is to stimulate and evaluate aspects of cognitive function such as attention (focused, sustained and alternating), memory and visuospatial function (immediate, working, episodic, semantic, spatial orientation, visual memory).
- Participant Feedback: At the end of the session, feedback will be collected from participants to improve future interactions of the exercise.

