5.3 Participating population

Source population: The source population of the study will be the patients who attend the cognitive rehabilitation program at the Centro Sociosanitario El Carme (CSSC) in Badalona Serviceis Asistencianals.

Location: El Carme Socio-Health Center (CSSC), Badalona, Spain.

Selection period: Participants will be selected from September to October 2023.

Inclusion criteria:

- Participants must be at least 60 years old, with no maximum age limit.
- Participants must be classified as having mild cognitive impairment with an MMSE score > 23.
- Participants must be currently attending cognitive rehabilitation sessions at the CSSC Day Hospital.
- Participants must be able to give informed consent or, in the event of incapacity, consent must be obtained from their legal representative.

- Exclusion criteria

- Patients with a serious or unstable illness that may interfere with their participation in the study.
- Patients with severe psychiatric disorders, such as psychotic disorders, delusions or hallucinations that may be exacerbated by the use of virtual reality.
- Patients with severe visual limitations that would prevent the use of virtual reality.
- The presence of eye diseases that cause blurred vision that cannot be corrected with contact lenses or glasses.
- Presence of hearing pathologies that cause a significant decrease in hearing without hearing aids.
- High sensitivity to motion sickness.
- Epileptic subject.
- Patients who are unable or unwilling to give informed consent.

Withdrawal criteria

Withdrawal criteria will include the appearance of health problems that may interfere with continued participation in the study, or withdrawal of consent by the participant.

Sampling type

The type of sampling will be non-probabilistic sequential. All patients who meet the inclusion criteria and do not meet any of the exclusion criteria will be invited to participate until the desired number of participants is reached.

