5.4 Study variables

5.4.1 Variables result, exposure or effect

Main Outcome Variable:

Acceptability and usability of VR exercises: This will be measured using a user satisfaction questionnaire and the System Usability Scale (SUS). HE will managen after the last session (the eighth).

Secondary Outcome Variables:

Cognitive function (memory and attention), measured through standardized tests: - Specific to attention and memory (Digits, TMT [Annex 3], SDMT [Annex 4]).

- General cognitive function tests:
- Montreal Cognitive Assessment (MoCA) [anexo 5]
- Mini-Mental State Examination (MMSE) [anexo 6]

The evaluations will be carried out before starting the training program and at the end of it (after the eighth session).

Usability of the system by professionals:

This will be evaluated using the System Usability Scale (SUS) for patients and professionals [Annex 7 and 8]. It will be administered to professionals after completing the training program.

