5.4.2 Other variables

- Age
- Sex
- Etiology of cognitive impairment
- Schooling
- Exposure to other treatments: Any additional medication or cognitive therapy that the patient is simultaneously participating in will be recorded.

5.5 Study Evaluations:

Visit	Procedures		
Selection visit (Pre-study)	Informed consent, collection of demographic data and results of cognitive function variables		
Visit 1 (Session 1)	Starting VR training sessions		
Visit 2 (Session 8 - Final)	Completion of the VR training sessions, questionnaires on cognitive function and satisfaction and usability variables.		

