6. SOURCES OF OBTAINING AND MANAGING DATA

6.1 Data source

Data collection in this pilot study will be carried out through primary sources. Data will be obtained directly from participants:

The acceptability and usability of the VR exercises will be measured through questionnaires that participants will complete after each VR session.

Cognitive function and quality of life will be measured through standardized tests that participants will complete before, during and after the VR training program.

Variables such as age, gender and degree of cognitive impairment will be collected through interviews and medical records.

Exposure to other treatments will be recorded through interviews with participants and review of their medical records.

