8. MANAGEMENT AND COMMUNICATION OF ADVERSE REACTIONS

As this study uses virtual reality in cognitive stimulation for patients with cognitive impairment and does not involve the use of medications, the management and communication of adverse drug reactions is not applicable in this context.

However, any adverse side effects associated with the use of virtual reality technology, such as dizziness, nausea or disorientation, will be carefully recorded and monitored by the research team. Healthcare professionals are trained to handle these incidents and will provide necessary care to study participants should these adverse effects occur.

The research team agrees to inform the collaborating company, Reality Telling, about any incident that occurs during the study, respecting the confidentiality of the participants. In the event of a serious adverse reaction, the research team will take necessary steps to ensure the safety of the participant and determine whether their participation in the study needs to be adjusted or discontinued.

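### Acceptability forms and post-baseline cognitive tests are tied to the session 8 visit, 6.1 gives another schedule, and nothing covers a patient who stops VR earlier

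*Combined protocol and SAP*

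**What the plan says.** Timing of the main outcome: 5.4.1 names a satisfaction questionnaire and the SUS and states "HE will managen after the last session (the eighth" as the time of administration.

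Timing of the cognitive tests: the same section says "The evaluations will be carried out before starting the training program and at the end of it (after the eighth session".

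Visit table: 5.5 has a selection visit, session 1 and session 8. The last row reads "Completion of the VR training sessions, questionnaires on cognitive function and satisfaction and usability variables". It has no row between sessions 1 and 8, and none for early termination.

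Data source: 6.1 says that acceptability and usability come from "questionnaires that participants will complete after each VR session", and cognition from "standardized tests that participants will complete before, during and after the VR training program".

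Stopping: the withdrawal criteria in 5.3 are "the appearance of health problems that may interfere with continued participation in the study" and withdrawal of consent. Section 8 adds that, after a serious adverse reaction, the team will "determine whether their participation in the study needs to be adjusted or discontinued". Neither section says what is then collected.

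Analysis: 5.7 describes SUS scores and compares cognitive scores by Student's t or Wilcoxon test. It defines no analysis set and no handling of missing forms. Section 5.6 fixes 20 patients, with no allowance for dropout and no replacement rule.

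**The concern.** Acceptability is the main objective (4.1). A patient who stops because the headset is unpleasant or frightening is informative on exactly that question. If staff work from 5.4.1 and 5.5, that patient is never asked, and a form not given at the time cannot be recovered later. Annex 7 even has an item on interrupting the simulation because of discomfort, but on this schedule only patients who reach session 8 would answer it.

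If staff work from 6.1 instead, forms exist up to the last session attended, but nothing says which of them is the endpoint. Two teams following the same protocol could therefore produce different main results.

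The result has uses beyond this pilot. Section 5.1 looks to possible incorporation in the Day Hospital programme, 7.1 promises to keep the tool in use if results are positive, and 5.7 intends the effect estimates for sizing later studies.

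**Working it through.** The plan has no figure to reproduce: 20 patients is a pragmatic choice with no effect size, SD, power or dropout rate behind it. The check is mainly a comparison of the text.

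**1. The two schedules**

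| Measure | 5.4.1 and 5.5 | 6.1 |
|---|---|---|
| Patient acceptability and usability | Once, after session 8 | After each session (up to 8 per patient) |
| Cognitive tests | Baseline and after session 8 | Baseline, during and after |

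Section 6.1 does not name the SUS, but it covers the same construct. No text says which schedule governs.

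**2. A patient who stops after, say, session 3**

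- Under 5.4.1 and 5.5: baseline cognition only, with no acceptability form and no post-baseline test.
- Under 6.1: three questionnaires and possibly a mid-programme test, with no rule on whether they count.
- Under 5.2: "At the end of the session, feedback will be collected from participants to improve future interactions of the exercise". This may help improve the exercise, but it is not defined as an outcome.
- Under 5.7: no rule for including or excluding the patient.

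**3. How likely is it that the gap matters?** The documents give no stopping risk, so a range is assumed. With independent risk q per patient, P(at least one stopper among 20) = 1 − (1 − q)^20.

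- q = 5%: 1 − 0.95^20 = 64%
- q = 10%: 1 − 0.90^20 = 88%
- q = 20%: 1 − 0.80^20 = 99%

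**4. Limit on what the missing forms leave open.** Annex 7 items have five response options. Scoring them 1 to 5 is an assumption, since the plan gives no scoring. With k of 20 starters lacking a form, the all-starter mean of an item is [(20 − k) × observed mean + sum of the k missing scores]/20. The missing sum lies between k and 5k, so the mean is undetermined within a width of 4k/20 = 0.2k points.

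- k = 1: 0.2; k = 2: 0.4; k = 5: 1.0
- If r of the k are recovered by a form at stopping, the width is 0.2(k − r). For k = 2 it is 0.4, 0.2 or 0 with r = 0, 1 or 2.

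This limit holds for any five-option item. It is not an estimate of bias.

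**5. Cognition.** The 95% half-width for mean change, in SDs of change, is t(0.975, n − 1)/√n.

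- n = 20: 2.093/4.472 = 0.47
- n = 18: 2.110/4.243 = 0.50
- n = 15: 2.145/3.873 = 0.55

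The loss of precision is modest, and no bias is calculated for cognition.

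**The case against.** The best reply is that the outcome section and the visit table agree, and that 6.1 is a general paragraph on data sources. It also mentions quality of life, for which 5.4 lists no measure, so 6.1 looks like the drafting slip. That is persuasive and decides which text to correct. It does not supply a rule for early stoppers.

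Stopping may also be rare. Section 5.3 excludes patients highly prone to motion sickness. Section 7.1 plans seated, supervised sessions, gentle content and gradual introduction, and the programme uses existing appointments over about four weeks (8 sessions at 2 per week). Stopping could be zero. This stands, and it is why no size is claimed.

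The study is a pilot with a descriptive main analysis, and section 8 records side effects whether or not a patient finishes. Both are true. But acceptability is the pilot's own main question, and a side-effect record does not capture a patient who simply dislikes VR.

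Finally, patients who dislike VR may leave by withdrawing consent, and a form at stopping would not reach them. This objection is sound. It is met only in part by separating the two decisions and by counting everyone who stops.

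Three stronger readings are tempting, but the documents do not support them:

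- That the result covers only patients who attended all eight sessions. The forms are tied to the final visit, and nothing excludes a patient who missed an earlier session but attends that one.
- That the result must be biased in favour of VR. Some stopping may reflect poor acceptability, but 5.3 also allows stopping for health problems, and no stopping rate or reasons are given.
- That section 8 is a general rule for discontinuation. It applies only after a serious adverse reaction.

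**Conclusion.** The point holds as a gap that should be closed before data collection. Sections 5.4.1 and 5.5 conflict with 6.1 on when patients are assessed. Under 5.4.1 and 5.5, the main result and the before-after cognitive change describe only patients who reach the final visit. The plan does not say so, and gives no rule for the others.

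The size and direction of the effect on the results are unknown. The probabilities of at least one stopper rest on assumed, independent risks. The 0.2-point limit per missing form rests on an assumed 1 to 5 scoring and is generic. Neither should be read as expected bias. What does not depend on any assumption is that, under 5.4.1 and 5.5, no acceptability form is planned for a patient who stops before the final visit.

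**What to change.** 1. **6.1:** remove the per-session timing of the questionnaires and the mid-programme cognitive testing, so that 6.1 matches 5.4.1 and 5.5. Adopting the 6.1 schedule instead would add up to seven form administrations per patient plus extra testing, and would need a rule on which form is the endpoint.
2. **5.3:** distinguish stopping VR from withdrawing consent to data collection.
3. **5.4.1 and 5.5:** give Annex 7 and the satisfaction questionnaire at stopping, or at the next Day Hospital appointment, to every patient who started session 1 and still consents to data collection. Where the patient still attends, give the cognitive battery when session 8 was due, about week 4.
4. **5.7:** report all starters with data beside those who reached the final visit, both labelled. Add the number out of 20 who stopped, at which session and why.

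The cost is a few sentences and no new instrument, because the forms and tests are already planned for all 20 patients. The downside is that some ratings will follow fewer than eight sessions, and averages may look less favourable. Patients who withdraw consent entirely or cannot be reached stay missing from the scores, but are still counted among those who stopped.

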5.4.2 Other variables

- Age
- Sex
- Etiology of cognitive impairment
- Schooling
- Exposure to other treatments: Any additional medication or cognitive therapy that the patient is simultaneously participating in will be recorded.

5.5 Study Evaluations:

Visit	Procedures		
Selection visit (Pre-study)	Informed consent, collection of demographic data and results of cognitive function variables		
Visit 1 (Session 1)	Starting VR training sessions		
Visit 2 (Session 8 - Final)	Completion of the VR training sessions, questionnaires on cognitive function and satisfaction and usability variables.		

5.6 Sample size

The sample size for this pilot study has been established at 20 patients. This decision is based on several factors:

Preliminary nature of the study: As this is a pilot study, the primary objective is to evaluate the usability and acceptability of the virtual reality intervention, rather than to demonstrate effectiveness. Pilot studies typically have smaller sample sizes than full studies.

Resources and capacity: The capacity of the El Carme Socio-Health Center in Badalona and the available resources (both in terms of staff and virtual reality equipment) also influence the sample size. Ensuring that each participant can receive appropriate care and support is

critical to accurate data collection and a positive patient experience.

Patient variability: Although the sample size is small, it is expected to reflect the diversity of the patient population in terms of severity of cognitive impairment, gender, age, etc. This diversity may provide a deeper understanding of how different types of patients may interact with virtual reality technology.

5.7 Statistical analysis

The data collected during the study will be analyzed using statistical methods appropriate for each type of variable. All analyses will be performed using statistical software SPSS 27.0.

Acceptability and Usability: Scores obtained on the System Usability Scale (SUS) will be analyzed descriptively to provide an overall measure of the acceptability and usability of the VR intervention.

Cognitive function: Depending on the normality of the variables, statistical tests will be applied to compare scores (parametric Student's T or non-parametric Wilcoxon (in the case of failure to comply with the assumption of normality).

Demographic and clinical variables: Correlation and multiple regression analyzes will be used to examine relationships between demographic and clinical variables (e.g., age, gender, etiology, education) and changes in acceptability, usability, cognitive function, and quality of life.

The hypotheses will be evaluated at the significance level of p < 0.05 (95% confidence level). As this is a pilot study, the results will be used primarily to generate hypotheses for future research and to provide effect size estimates that may be useful for sample size calculation in future studies.

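### The documents disagree on when the acceptability questionnaire is given, and if it is given only at session 8, patients who stop early fall out of the main result

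*Combined protocol and SAP*

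**What the plan says.** The main outcome in 5.4.1 is acceptability and usability: "This will be measured using a user satisfaction questionnaire and the System Usability Scale (SUS". The same section places administration "after the last session (the eighth". The visit table in 5.5 agrees: its session 8 row is the only one that lists "questionnaires on cognitive function and satisfaction and usability variables".

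Section 6.1 gives a different schedule: "The acceptability and usability of the VR exercises will be measured through questionnaires that participants will complete after each VR session".

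In 5.7 the main analysis is: "Scores obtained on the System Usability Scale (SUS) will be analyzed descriptively to provide an overall measure of the acceptability and usability". A later paragraph of 5.7 plans correlation and multiple regression of demographic and clinical variables against "changes in acceptability, usability, cognitive function, and quality of life".

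The forms are cited in 5.4.1 under the professionals' outcome: "This will be evaluated using the System Usability Scale (SUS) for patients and professionals [Annex 7 and 8". Annex 7 (patients) prints two blocks of 8 items, one headed System usability scale and one rating the headset. Annex 8 (professionals) prints 8 and 3.

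Section 5.3 allows withdrawal for health problems that interfere with participation, or for withdrawn consent. No questionnaire at withdrawal is described.

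**The concern.** The sections cannot all be followed. One form at the end and one form after each of 8 sessions are different data collections, and only the second supports an analysis of change.

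The choice decides who is counted. With a form at session 8 only, a patient who leaves sooner contributes nothing to acceptability. Section 7.1 says some patients may have dizziness or disorientation, and 5.3 withdraws patients for health problems, so stopping can be related to how acceptable the programme was. A completers-only summary could then look better than the experience of everyone who started. A form that was never given to a patient who left cannot be recovered at analysis.

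**Working it through.** **1. Timing, side by side**

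| Place | Schedule stated or implied | Forms from a patient who completes all 8 sessions | Forms from a patient who attends 3 sessions |
|---|---|---|---|
| 5.4.1 | after session 8 | 1 | 0 |
| 5.5 visit table | session 8 row only | 1 | 0 |
| 6.1 | after each session | 8 | 3 |
| 5.7, changes in acceptability and usability | at least two forms | 2 or more | 2 or more |

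Sections 5.4.1 and 5.5 agree with each other and conflict with 6.1. The wording on changes in 5.7 fits 6.1 and does not fit 5.4.1 or 5.5.

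**2. What is held on an early stopper under the session-8 schedule**

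Section 8 records side effects such as dizziness and nausea, and section 5.2 collects feedback at the end of the video sessions. Neither is part of the acceptability analysis in 5.7. That analysis would therefore contain nothing from this patient.

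**3. Possible size (illustration only)**

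The documents give 20 patients (5.6). They give no dropout rate, expected score or SD. Assumed: k = 2, 4 or 6 early stoppers, completers' mean 75 on a 0-100 scale, and stoppers' mean s = 25 or 50 had they been asked.

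Mean over all 20 = [75(20 − k) + s·k]/20 = 75 − (k/20)(75 − s)

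| k | s = 25 | s = 50 | Completers only | Overstatement |
|---|---|---|---|---|
| 2 | 75 − 0.1 × 50 = 70 | 75 − 0.1 × 25 = 72.5 | 75 | 2.5 to 5 |
| 4 | 75 − 0.2 × 50 = 65 | 75 − 0.2 × 25 = 70 | 75 | 5 to 10 |
| 6 | 75 − 0.3 × 50 = 60 | 75 − 0.3 × 25 = 67.5 | 75 | 7.5 to 15 |

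The difference is (k/20)(75 − s). It is zero if nobody stops, or if stoppers would have answered like completers (s = 75).

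**4. Item direction, for the accompanying clarification**

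Read from the wording in Annex 7, the unfavourable items are simulation 2, 5 and 8 and headset 1 to 7, which is 3 + 7 = 10 of 16. The plan does not state that they are reversed, or whether the headset block enters the score.

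**The case against.** The strongest reply is that 5.4.1 and 5.5 state the schedule clearly and 6.1 is a loose summary. Section 6.1 also has cognitive tests taken during the programme, whereas 5.4.1 has them only before and after. The wording on changes in 5.7 sits in a list that includes quality of life, for which 5.4.1 names no instrument, so it is thin evidence of a repeated-measures plan. This may well be right about the intention. It does not remove the conflict, and if session 8 is what was meant, the early-stopper problem applies in full.

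A second reply is that dropout may be small. The course is 8 sessions at two a week (8/2 = 4 weeks), 5.3 excludes patients highly sensitive to motion sickness, and 7.1 plans static or smooth-motion content. Withdrawals may also have nothing to do with VR. All of this stands. It limits the likely size, and it is why the figures above are assumptions. Side effects in stoppers are recorded too, though outside the acceptability result.

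Some stronger readings are tempting and are not supported:

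- A reader might infer that the plan gives no item set. The items are printed in both annexes, and the first block carries the scale's name. What is missing is a sentence confirming the primary block and the reversal.
- A reader might infer that the score will be computed with items unreversed or blocks pooled. The documents propose neither, and collected answers can be re-keyed later.
- A reader might infer that the headset block already measures the side effects named in 7.1. Only headset item 5 asks about dizziness, and none asks about disorientation.
- A reader might infer that an acceptance benchmark is required because 5.7 says "The hypotheses will be evaluated at the significance level of p < 0.05 (95% confidence level". The same section makes the acceptability analysis descriptive and the study mainly hypothesis-generating, so the lack of a benchmark, like the unstated summary of the satisfaction questionnaire, is unwritten detail.

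**Conclusion.** The point holds in two parts. The contradiction on timing stands without assumption: 5.4.1 and 5.5 conflict with 6.1, and the analysis of changes in 5.7 cannot be done from one form. The loss of early stoppers is conditional. It follows only if the form is given at session 8 alone; under 6.1, a patient who completes at least one session has a form.

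Its size cannot be taken from the documents. Under the stated assumptions the completers-only mean overstates the all-patient mean by 2.5 to 15 points. The upward direction rests on stoppers being less favourable than completers, which is plausible given 5.3 and 7.1 but not shown. A reader might infer that the main result is biased; the documents support only that it could be, and that the plan has no means of finding out. This should be fixed, because it concerns the main objective and the missing forms cannot be collected later.

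**What to change.** 1. Reconcile 5.4.1, 5.5 and 6.1 on when the questionnaire is given, and bring 5.7 into line.
   - *If session 8 only is kept:* ask patients who stop early and still consent to complete the form at their last session. Include those forms in the primary summary and report how many enrolled patients have no form. Delete the reference to changes for acceptability and usability in 5.7.
   - *If after each session is kept:* use the session 8 form, or the form from the last session attended, as primary. Define change as that form minus session 1. A patient with one session then has a primary score but no change.
2. As a minor clarification, state before analysis that the patient block headed System usability scale is primary, that simulation items 2, 5 and 8 and headset items 1 to 7 are reversed, that the headset block is reported separately, and that patients and professionals are analysed separately. Report the mean with its 95% CI.

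Cost: short edits to those sections and a scoring line for the annexes. No new items or patients are needed. Under the session-8 schedule there is one extra form per consenting early stopper; under the each-session schedule there is none beyond those already described. Some forms will still be missing where consent is withdrawn.

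### Section 6.1 collects the patient acceptability and usability forms after every session, 5.4.1 and 5.5 only after session 8, and the regression on changes in 5.7 has no data under the latter

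*Combined protocol and SAP*

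**What the plan says.** Acceptability to patients is the main objective (4.1). Four places in the combined protocol and SAP bear on when it is measured and how it is used.

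- **5.4.1** names a satisfaction questionnaire and the SUS as the main-outcome instruments and times them "after the last session (the eighth"). The verb in that sentence is garbled in translation, but the timing is legible.
- **5.5** lists "questionnaires on cognitive function and satisfaction and usability variables" at Visit 2 (Session 8) only. No satisfaction or usability form appears at the selection visit or at Session 1.
- **6.1** states: "The acceptability and usability of the VR exercises will be measured through questionnaires that participants will complete after each VR session".
- **5.7** states: "Scores obtained on the System Usability Scale (SUS) will be analyzed descriptively to provide an overall measure of the acceptability and usability". It does not say which administration is meant. It then relates demographic and clinical variables to "changes in acceptability, usability, cognitive function, and quality of life" by correlation and multiple regression.

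The cognitive tests show a similar mismatch. Section 5.4.1 places them "before starting the training program and at the end of it (after the eighth session"), whereas 6.1 has them "before, during and after the VR training program".

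**The concern.** The three statements of timing cannot all be followed. A change needs at least two measurements on the same patient, and the section that defines the outcome provides one. If 6.1 is followed instead, there are several measurements and no rule for turning them into the single overall measure that 5.7 describes. First impression, final opinion and an average over sessions would all be defensible, and the choice could be made after the data are seen.

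The timing also affects whom the main result describes. Section 5.3 foresees withdrawal for health problems and withdrawal of consent. If the only form is given after session 8, a patient who stops earlier leaves no acceptability or usability answers. Such patients may well be less accepting than those who finish, although the documents offer no data on this. Section 8 has VR side effects recorded separately, so those are not lost, but these patients' answers on acceptability and usability are.

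**Working it through.** The plan states no figure that depends on this point. The sample size in 5.6 rests on the pilot nature of the study and on resources, so there is no calculation to reproduce. The check is a count.

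**Inputs.** Patients: 20 (5.2, 5.6). Sessions: 8 (5.2). Administrations per patient: 1 under 5.4.1 and 5.5; up to 8 under 6.1.

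**Forms** = patients × administrations.

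- 5.4.1 and 5.5: 20 × 1 = 20.
- 6.1: 20 × 8 = up to 160.

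**Consecutive changes available per patient** = administrations − 1.

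- 5.4.1 and 5.5: 1 − 1 = 0, so the regression on changes has 0 observations for acceptability and usability.
- 6.1: 8 − 1 = up to 7 consecutive changes, or one last-minus-first change. The latter gives up to 20 values, one per patient. The first form follows session 1, so none of these is a change from a pre-VR baseline.
- Cognitive tests under 5.4.1, for comparison: 2 − 1 = 1 change per patient, up to 20 in all. For these outcomes the wording of 5.7 works.

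**Does another section settle it?** Section 5.2 collects feedback at the end of the video session, but its purpose is to improve the exercise and it is not tied to either main-outcome instrument. Section 6.1 speaks of questionnaires that measure acceptability and usability. The two are not the same, so 5.2 does not reconcile 6.1 with 5.4.1.

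**Early leavers (illustration only).** Let *d* of the 20 patients leave before session 8, with only session-8 forms collected. Then

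mean of all 20 − mean of completers = (*d*/20) × (mean of leavers − mean of completers).

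If *d* is 1 to 4 (an assumption), 19 to 16 patients supply a form, and the completers' mean differs from the mean of all enrolled by 0.05 to 0.20 of the gap between leavers and completers. The documents give neither *d* nor that gap, so no bias can be computed.

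**The case against.** The best defence is that the plan's two defining sections agree. Section 5.4.1 defines the outcome, 5.5 is the visit schedule, and both say session 8. Section 6.1 is a general account of data sources and is loosely written: it also departs from 5.4.1 on the cognitive tests and mentions quality of life, for which 5.4 names no instrument. The main analysis is descriptive and can be run on 20 session-8 forms without any change score. In a rough translation, *changes* in the secondary regression sentence may simply mean score levels.

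Much of this stands. 6.1 is the outlier and the main descriptive analysis is feasible. But 6.1 is explicit about after-session questionnaires, and staff following it would collect different data. Nothing in 5.7 signals that *changes* means something else for acceptability, and cognitive function, in the same list, has a true before-after change.

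A reader might infer more than the documents support:

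- *That the main score has no defined source, or that the two schedules have equal standing.* They do not: 5.4.1 and 5.5 agree.
- *That the schedule alone decides who is counted.* It does not. If forms were collected every session but the session-8 form were the main score, early leavers would still be missing. The summary rule matters as well.
- *That acceptability will be overstated by a calculable amount.* Any such figure needs an assumed drop-out and assumed answers from leavers. 5.7 also plans no percent-favourable endpoint.
- *That the SD passed on to future studies will be wrong.* A mean of eight forms has an SD √((1 + 7r)/8) times that of one form: 0.62 to 0.86 for an assumed between-session correlation r of 0.3 to 0.7. But no section proposes that mean, and the intention to "provide effect size estimates that may be useful for sample size calculation in future studies" is not tied to acceptability.

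Item coding, reversal of negatively worded items, and whether the satisfaction questionnaire is a separate form are distinct questions about the instrument and are not part of this point.

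**Conclusion.** The concern holds as a contradiction in timing with one analytical consequence. Sections 5.4.1 and 5.5 give 20 forms and no change scores, so the planned regression on changes in acceptability and usability cannot be run as written. Section 6.1 gives up to 160 forms, with no rule for the main score or for change. These counts rest only on the stated 20 patients and 8 sessions, and confidence in them is high.

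With a session-8-only form, the main result applies to patients who reached and completed that form. This limits what can be concluded but does not demonstrate bias, whose size is unknown. The sample size is not affected. The point should be corrected because it concerns the main objective. It does not invalidate a descriptive, uncontrolled pilot.

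**What to change.** 1. Make 5.4.1, 5.5 and 6.1 state one schedule for the patient forms. The simplest correction is to bring 6.1 into line with 5.4.1 and 5.5, and to align its timing of the cognitive tests in the same edit.
2. *If once:* in 5.7, replace changes in acceptability and usability with the session-8 score, and keep changes for the cognitive tests measured before and after. *If after each session:* list the forms in 5.5, name the one that gives the main score, define the change (for example last minus first), and use one value per patient or a repeated-measures model.
3. Invite patients who stop early to complete Annex 7 at their last attended session, except those who withdraw consent to further data collection. Say how these exit forms are used, and report the numbers enrolled, completing and leaving early, with reasons, beside the score.

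The cost is wording in four sections, a few exit forms and slightly more reporting. The per-session option costs more: up to 160 forms instead of 20, from patients with cognitive impairment. If collection has ended, state which schedule was followed and report the score as applying to those who completed the form.
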